7.2. Screening and Critical Baseline Assessments

After written, informed consent, screening assessments will be performed. Screening procedures are outlined in the Time and Events Table (Section 7.1). All screening assessments must be performed within 4 weeks of Day 1 (except for subjects being treated with azathioprine or leflunomide, where written informed consent for the study must be obtained prior to discontinuing these drugs and beginning the screening period). Women and men of reproductive potential must consent to use of a highly effective method of contraception for the period predefined in [Appendix 2](#).

- The following demographic parameters will be captured: year of birth, sex, race and ethnicity.
- Medical/medication/family history will be assessed as related to the inclusion/exclusion criteria listed in Section 5.
- Cardiovascular medical history/risk factors (as detailed in the eCRF) will be assessed at screening.
- Rheumatoid arthritis history – disease duration, medication history, RA functional class (I, II or III) will be confirmed.
- The following examination, confirmation and test will be conducted.
 - Physical examination (complete examination at screening, and brief examination at Day 1 visit; see Section 7.4.7).
 - Vital signs including temperature, systolic and diastolic blood pressure, pulse rate, and respiratory rate.
 - Triplicate 12-lead ECG (screening only).
 - Chest X-ray (posterior to anterior [PA] and lateral, or in accordance with local requirements) (screening only).
 - If a chest X-ray has been taken within the past 12 weeks that shows no clinically-significant abnormality, and there are no signs or symptoms suggestive of pulmonary disease that would exclude the subject, then a further chest X-ray is not required.
 - Spirometry FEV₁, FVC and DLCO (see SRM for additional details) (screening only).
 - Baseline chest HRCT for subjects with DLCO values between $\geq 60\% - < 70\%$, and it is recommended that the subject will be reviewed by a local pulmonologist to exclude significant pre-existing respiratory disease.
 - Cough, Lung Auscultation, Pulse Oximetry, Borg Dyspnea Scale.
 - AEs reporting and recording of concomitant medications.
- Blood samples will be taken for:
 - Hematology.
 - Biochemistry.

- Serum beta subunit human chorionic gonadotropin (β hCG) pregnancy test (screening only).
- HIV antibody, Hepatitis B surface antigen, anti-HBc, and Hepatitis C antibody testing (screening only).
- CRP.
- ESR (baseline only).
- Cholesterol, triglycerides, high density lipoprotein (HDL) and low density lipoprotein (LDL) (baseline only).
- Autoimmune serology: RF and ACPA (i.e., anti-CCP antibodies) (screening only).
- T-spot test for TB (screening only).
- Exploratory GM-CSF, PD, lung biomarkers and anti-GM-CSF auto-antibodies (baseline only).
- PK samples and immunogenicity (anti-GSK3196165 antibody) (baseline only).
- RNA (in consenting subjects) (baseline only).
- Pharmacogenomic DNA (in consenting subjects) (baseline only).
- Urine sample will be taken for:
 - Routine urinalysis (screening only).
 - Urine β hCG pregnancy test (baseline only).
- Disease activity assessments (see Section 7.6) and Patient-reported outcome (PRO) questionnaires (see Section 7.9):
 - Tender joint count (68 joints).
 - Swollen joint count (66 joints).
 - Patient's Assessment of Arthritis Pain.
 - Patient's Global Assessment of Arthritis.
 - Physician's Global Assessment of Arthritis.
 - HAQ-DI.
 - FACIT-Fatigue (baseline only).

Patient-reported outcomes questionnaires should be completed by subjects before any other assessment at a clinic visit, in the order specified in the SRM.

7.3. Pharmacokinetics

Blood samples for pharmacokinetic analysis of GSK3196165 will be collected at the time points indicated in the Time and Events Table (Section 7.1). The actual date and time of each blood sample will be recorded. The timing of PK samples may be altered and/or PK

samples may be obtained at additional time points to ensure thorough PK monitoring. Details of PK blood sample collection, processing, storage and shipping procedures are provided in the SRM.

Sample analysis will be performed under the control of GSK. Concentrations of GSK3196165 will be determined in serum samples using the currently approved bioanalytical methodology for samples in GSK3196165 group, but not in placebo group. Raw data will be archived at the bioanalytical site (detailed in the SRM).

PK analyses are described in Section 9.4.1 and Section 9.4.5.1.

7.4. Safety

Planned time points for all safety assessments are listed in the Time and Events Table (Section 7.1).

7.4.1. Study visits

Subjects will have systematic safety monitoring throughout the study. Additional time points for safety tests (such as vital signs, physical exams and laboratory safety tests) may be added during the course of the study based on newly available data to ensure appropriate safety monitoring.

In addition to routine laboratory assessments, ECG monitoring, and evaluation of adverse events, particular attention will be paid to respiratory events and function given the potential risk associated with targeting GM-CSF and the effects on alveolar macrophages. This may result in the occurrence of the extremely rare condition of PAP, which is characterized by the accumulation of surfactant lipids and protein in the alveolar spaces (with no fibrosis), with resultant impairment in gas exchange, which may lead to increase a risk of secondary pulmonary infections.

All subjects will return for a follow-up visit at 10 weeks after completion/withdrawal of treatment period. Particular attention will be paid to withdrawal symptoms given the potential risk associated with release of immune suppression.

7.4.2. Safety endpoints and other assessments

- Incidence of AEs/SAEs.
- Incidence of AESI (such as serious infections and opportunistic infections) (see Section 7.4.5).
- Pulmonary events (cough, dyspnea, pulse oximetry, spiroometry, D_{LCO}).
- Lung biomarkers (such as SP-D, KL-6, cholestenoneic acid).
- ECG measurements.
- Vital signs.
- Hematological and clinical chemistry parameters.

- Physical examinations.
- Pregnancy test (for women of child-bearing potential).
- Immunogenicity (anti-GSK3196165 antibody).

7.4.3. Adverse Events (AEs) and Serious Adverse Events (SAEs)

The definitions of an AE or SAE can be found in [Appendix 5](#).

The investigator and their designees are responsible for detecting, documenting and reporting events that meet the definition of an AE or SAE.

7.4.3.1. Time period and Frequency for collecting AE and SAE information

- AEs and SAEs will be collected from the start of Study Treatment until the follow-up contact (12 weeks after the last dose of investigational product), at the timepoints specified in the Time and Events Table (Section [7.1](#)).
- Medical occurrences that begin prior to the start of study treatment but after obtaining informed consent may be recorded on the Medical History/Current Medical Conditions section of the eCRF.
- Any SAEs assessed as related to study participation (e.g., protocol-mandated procedures, invasive tests, or change in existing therapy) or related to a GSK product will be recorded from the time a subject consents to participate in the study up to and including any follow-up contact.
- All SAEs will be recorded and reported to GSK within 24 hours, as indicated in [Appendix 5](#).
- Investigators are not obligated to actively seek AEs or SAEs in former study subjects. However, if the investigator learns of any SAE, including a death, at any time after a subject has been discharged from the study, and he/she considers the event reasonably related to the study treatment or study participation, the investigator must promptly notify GSK.

NOTE: The method of recording, evaluating and assessing causality of AEs and SAEs plus procedures for completing and transmitting SAE reports to GSK are provided in [Appendix 5](#).

7.4.3.2. Method of Detecting AEs and SAEs

Care will be taken not to introduce bias when detecting AEs and/or SAEs. Open-ended and non-leading verbal questioning of the subject is the preferred method to inquire about AE occurrence. Appropriate questions include:

- “How are you feeling?”
- “Have you had any (other) medical problems since your last visit/contact?”
- “Have you taken any new medicines, other than those provided in this study, since your last visit/contact?”

7.4.3.3. Follow-up of AEs and SAEs

After the initial AE/SAE report, the investigator is required to proactively follow each subject at subsequent visits/contacts. All SAEs, and non-serious AEs of special interest (as defined in Section 7.4.5) will be followed until resolution, until the condition stabilizes, until the event is otherwise explained, or until the subject is lost to follow-up (as defined in Section 5.4). Further information on follow-up procedures is given in [Appendix 4](#).

7.4.3.4. Cardiovascular and Death Events

For any cardiovascular events detailed in [Appendix 5](#) and all deaths, whether or not they are considered SAEs, specific Cardiovascular (CV) and Death sections of the eCRF will be required to be completed. These sections include questions regarding cardiovascular (including sudden cardiac death) and non-cardiovascular death.

The CV eCRFs are presented as queries in response to reporting of certain CV MedDRA terms. The CV information should be recorded in the specific cardiovascular section of the eCRF within one week of receipt of a CV Event data query prompting its completion.

The Death eCRF is provided immediately after the occurrence or outcome of death is reported. Initial and follow-up reports regarding death must be completed within one week of when the death is reported.

7.4.4. Laboratory and Other Safety Assessment Abnormalities Reported as AEs and SAEs

Any abnormal laboratory test results (hematology, clinical chemistry, or urinalysis) or other safety assessments (e.g., ECGs, vital signs measurements), including those that worsen from baseline, and felt to be clinically significant in the medical and scientific judgement of the investigator are to be recorded as AEs or SAEs.

However, any clinically significant safety assessments that are associated with the underlying disease, unless judged by the investigator to be more severe than expected for the subject's condition, are not to be reported as AEs or SAEs.

7.4.5. AEs of Special Interest

Please see Section 4.6.1 for a discussion of potential risks with GSK3196165. AEs of special interest include:

- Serious infections, including serious respiratory infections and TB.
- Opportunistic infections.
- Neutropenia (grade 3 or 4).
- Respiratory events including:
 - Persistent (for 3 consecutive weeks) reduction in $D_{LCO} >15\%$.
 - Persistent (for 3 consecutive weeks) cough and/or dyspnea.

- Non life threatening pulmonary changes related to surfactant accumulation.
- PAP.
- Hypersensitivity reactions, including anaphylaxis.
- Injection site reactions.

7.4.5.1. Disease-Related Events and/or Disease-Related Outcomes Not Qualifying as SAEs

The following have been specified as disease-related events (DREs) for the study:

- Events related to exacerbation of articular/peri-articular manifestations of RA, will not be reported as AEs, and will be recorded in the DRE eCRF.
- Events related to the articular/peri-articular flare up of the disease, and that require hospitalization, will not be reported as SAEs. However, such events must still be recorded in the DRE eCRF.

These DREs will be monitored by a Safety Review Team (SRT) on a routine basis.

NOTE: However, if either of the following conditions apply, then the event must be recorded and reported as an SAE (instead of a DRE):

- *The event is, in the investigator's opinion, of greater intensity, frequency, or duration than expected for the individual subject.*

OR

- *The investigator considers that there is a reasonable possibility that the event was related to treatment with the investigational product.*

New onset or worsening of extra-articular manifestations of RA should be reported as AEs/SAEs.

7.4.5.2. Regulatory Reporting Requirements for SAEs

Prompt notification by the investigator to GSK of SAEs and non-serious AEs related to study treatment (even for non- interventional post-marketing studies) is essential so that legal obligations and ethical responsibilities towards the safety of subjects and the safety of a product under clinical investigation are met.

GSK has a legal responsibility to notify both the local regulatory authority and other regulatory agencies about the safety of a product under clinical investigation. GSK will comply with country specific regulatory requirements relating to safety reporting to the regulatory authority, Institutional Review Board (IRB)/Independent Ethics Committee (IEC) and investigators.

Investigator safety reports are prepared for suspected unexpected serious adverse reactions according to local regulatory requirements and GSK policy and are forwarded to investigators as necessary.

An investigator who receives an investigator safety report describing a SAE(s) or other specific safety information (e.g., summary or listing of SAEs) from GSK will file it with the GSK3196165 IB and will notify the IRB/IEC, if appropriate according to local requirements.

7.4.6. Pregnancy

- Any pregnancy (participating females and female partners of participating males) that occurs from first administration of investigational product to the follow-up visit must be reported.
- To ensure subject safety, each pregnancy must be reported to GSK within 2 weeks of learning of its occurrence and should follow the procedures outlined in [Appendix 6](#).

7.4.7. Physical Exams

- A complete physical examination at the Screening visit will include, at a minimum, assessment of the Cardiovascular, Respiratory, Gastrointestinal and Neurological systems. Height and weight will also be measured and recorded.
- A brief physical examination at subsequent assessments will be performed as indicated in the Time and Event Table (Section [7.1](#)) and include, at a minimum assessments of the skin, lungs, cardiovascular system, and abdomen (liver and spleen). Body weight will also be measured and recorded.
- Investigators should pay special attention to clinical signs related to previous serious illnesses.

7.4.8. Vital Signs

- Vital signs will be performed prior to dosing with GSK3196165.
- Vital signs will be collected as indicated in the Time and Event Table (Section [7.1](#)).
- Vital signs will be measured after 5 minutes rest and will include temperature, systolic and diastolic blood pressure, pulse rate and respiratory rate.
- A single set of values will be collected and recorded in the source documentation and eCRF.

7.4.9. Electrocardiogram (ECG)

- Triplicate 12 lead ECGs will be obtained at screening, then single 12 lead ECGs will be obtained at the time points after Day 1 presented in the Time and Events Table (Section [7.1](#)) during the study using an ECG machine that automatically calculates the heart rate and measures PR, QRS, QT, and QTc intervals. The ECG may be repeated in triplicate if the recorded QTcF value is out of range. The QTc should then be based on averaged QTc values of the triplicate ECGs obtained over a brief recording period (e.g., 5-10minutes). Refer to Section [5.4.2](#) for QTc withdrawal criteria and additional QTc readings that may be necessary.

7.4.10. Clinical Safety Laboratory Assessments

All protocol required laboratory assessments, as defined in [Table 3](#), must be conducted in accordance with the Laboratory Manual, and Protocol Time and Events Schedule (Section 7.1). Laboratory requisition forms must be completed and samples must be clearly labelled with the subject number, protocol number, site/centre number, and visit date. Details for the preparation and shipment of samples will be provided by the laboratory and are detailed in the Central Laboratory Manual. Reference ranges for all safety parameters will be provided to the site by the laboratory responsible for the assessments.

If additional non-protocol specified laboratory assessments are performed at the institution's local laboratory and result in a change in subject management or are considered clinically significant by the investigator (e.g., SAE or AE or dose modification) the results must be recorded in the eCRF.

Refer to the central laboratory manual for appropriate processing and handling of samples to avoid duplicate and/or additional blood draws.

All study-required laboratory assessments will be performed by a central laboratory, apart from:

- ESR: The results of each test must be entered into the eCRF.

Hematology, clinical chemistry, urinalysis and additional parameters to be tested are listed in [Table 3](#).

Table 3 Routine Laboratory Assessments

Hematology	Biochemistry	Urinalysis
Hemoglobin	Sodium	Urine dipstick
Hematocrit	Potassium	Glucose
Mean corpuscular volume (MCV)	Calcium	Protein
Mean corpuscular hemoglobin (MCH)	Phosphate	
Mean corpuscular hemoglobin concentration (MCHC)	Urea nitrogen	
Erythrocyte count	Creatinine	Microscopy of urine sediment for erythrocytes, leukocytes and casts if urine dipstick abnormal
Reticulocyte count	Creatinine clearance (calculated)	
Leukocyte count	Aspartate transaminase (AST)	
Leukocyte differential count	Alanine transaminase (ALT)	
neutrophils	γ -glutamyl transpeptidase (GGT)	
eosinophils	Lactate dehydrogenase (LDH)	Urine pregnancy test
basophils	Alkaline phosphatase (ALP)	
monocytes	Bilirubin (total)	
lymphocytes	Creatine Phosphokinase (CPK)	
Platelets	Total protein	
Activated partial thromboplastin time (aPTT)		
Prothrombin Time (PT)		

Hematology	Biochemistry	Urinalysis
International Normalised Ratio (INR) Fibrinogen Erythrocyte Sedimentation Rate (ESR)*	Albumin Albumin/globulin ratio Glucose C-reactive protein (CRP) Cholesterol** Triglycerides** High-density lipoprotein (HDL)** Low-density lipoprotein (LDL)** Pregnancy test	

*Measured locally

**Fasting tests

All laboratory tests with values that are considered clinically-significantly abnormal during participation in the study or within 12 weeks after the last dose of study treatment should be repeated until the values return to normal or baseline. If such values do not return to normal within a period judged reasonable by the investigator, the etiology should be identified and the sponsor notified.

Serum will be collected at baseline and throughout the study to measure potential biomarkers of lung damage such as SP-D, KL-6 and cholestenoneic acid (see Section 7.7). Baseline measurement of GM-CSF autoantibodies will be measured.

7.4.11. Pulmonary Assessments

Pulmonary assessments are a key aspect of the safety monitoring in this study.

The following pulmonary assessments will be performed at the time points presented in the Time and Events Table (Section 7.1).

- Chest X ray
- Cough
- Borg dyspnea questionnaire
- Lung auscultation
- Pulse oximetry
- PFTs – spirometry (FEV₁, FVC), gas transfer (D_{LCO})

Further details of this assessment are provided in the SRM.

In the event of any new or clinically significant pulmonary abnormalities that may develop during the study (e.g., increased shortness of breath/dyspnea, or unexplained and persistent coughing), the subject should be referred to a pulmonologist for further assessment. The study treatment should be suspended until the symptoms or signs that

caused referral have resolved and/or the underlying diagnosis has been determined and clinically significant events have been excluded by the pulmonologist.

Additional pulmonary imaging (HRCT) or other tests may be performed on a subject during the study to investigate pulmonary abnormalities, and the SRT may request copies of any reports or images for central review.

7.5. Immunogenicity

Serum samples will be collected and tested for presence of antibodies that bind to GSK3196165. Serum samples for testing anti-GSK3196165 antibodies will be collected as described in Section 7.1, Time and Events Table. The actual date and time of each blood sample collection will be recorded. Details of blood sample collection (including volume to be collected), processing, storage and shipping procedures are provided in the Study Reference Manual (SRM).

The timing and number of planned immunogenicity samples may be altered during the course of the study, based on newly-available data to ensure appropriate safety monitoring. In the event of a hypersensitivity reaction that is either 1) clinically-significant in the opinion of the investigator, or 2) leads to the subject withdrawing from the study, blood samples should be taken from the subject for immunogenicity testing, at the time of the event and again 12 weeks after. For subjects who prematurely withdraw from the study, immunogenicity testing will occur at withdrawal and at follow-up 12 weeks after last dose.

Serum will be tested for the presence of anti-GSK3196165 antibodies using the currently approved analytical methodology using a tiered testing schema: screening, confirmation and titration steps. The presence of treatment emergent anti-drug antibodies (ADA) will be determined using a GSK3196165 bridging style ADA assay with a bio-analytically determined cut point determined during assay validation. Samples taken after dosing with GSK3196165 that have a value at or above the cut-point will be considered treatment-emergent ADA-positive. These ADA positive samples will be further evaluated in a confirmatory assay, and confirmed positive samples will be further characterized by assessment of titer. Results of anti-GSK3196165 antibody testing will be reported at the end of the study and will include incidence and titer. The presence or absence of antibodies to GSK3196165 in dosed subjects will be analyzed, then summarized descriptively and/or graphically presented.

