4.2. Treatment Arms and Duration

This study is composed of up to 4 weeks screening period, 12 weeks treatment period (last dose Week 10), and 10 weeks follow-up period (12 weeks from last dose).

Subjects will be randomized (1:1:1:1) to placebo or one of three subcutaneous (SC) GSK3196165 doses at Day 1 (Week 0).

Treatment with GSK3196165 or placebo will be given weekly as a single SC injection by an unblinded administrator. There will be 5 weekly injections (Day 1, 8, 15, 22, 29), then every other week (EOW) injections at Day 43, 57 and 71 (Week 6, 8, 10, respectively).

GSK3196165/placebo must be administered on the same day each week ± 1 day for the first 5 weekly doses. Following this GSK3196165 or placebo must be administered on the same day EOW ± 3 days.

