Rhesus Monkey 26 week IV	Week 26	5 ^d	2822	5644	1.8	2.9	
		15	11264	22528	7.3		
		50 ^c	24482	48963	15.9		
Human 12 weeks SC ^e		Last dose in Induction phase (Week 4-5)	1536	-	15.9		
		Last dose in Maintenance phase (Week 10-12)	-	1930			

IV intravenous; SC subcutaneous

a. AUC(0-168): As there were no significant differences on sampling occasions or gender differences within each primate study, the end of study mean values of AUC (0-168) in female and male [GSK3196165 IB: Table 10 and Table 11 in Section 4.5] have been used and divided by 2.

b. AUC(0-336): AUC (0-168) have been multiplied by 2 to obtain mean concentrations over a two week period.

c. No observed adverse effect level (NOAEL).

d. No observed effect dose level (NOEL).

e. Simulated median AUC based on analysis of SC data from study MOR103C104 with a 2 compartment PK model.

The dose range includes doses that are anticipated to be effective or minimally effective based on the results as follows:

- In the Phase 1b/2a RA study (Study MSC-1001), IV doses of 1.0 mg/kg and 1.5 mg/kg showed activity and 0.3 mg/kg showed little to no activity after 4 weeks of weekly treatment (see GSK3196165 IB).
- Complete inhibition of GM-CSF function by GSK3196165 has been observed in different assays *in vitro* at mean concentrations averaging 0.2 μ g/mL. Although the level of penetration of GSK3196165 into the inflamed synovial tissues is not known, it is reasonable to assume that its penetration rate is in the range as seen with other mAbs. Concentration levels of mAbs in the synovium vary among patients and have been reported to be below 30% of the plasma values [Choy, 2000]. Based on a 30% penetration rate, the continuous GM-CSF production and considering patient heterogeneity, the minimal or sub-optimal clinical effect level is anticipated to be at approximately 10-fold higher (2 μ g/mL) than the inhibitory concentration derived from *in vitro* studies.

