7. STUDY ASSESSMENTS AND PROCEDURES

Protocol waivers or exemptions are not allowed with the exception of immediate safety concerns. Therefore, adherence to the study design requirements, including those specified in the Time and Events Table, are essential and required for study conduct.

This section lists the procedures and parameters of each planned study assessment. The exact timing of each assessment is listed in the Time and Events Table (Section [7.1](#)).

The following points must be noted:

- If assessments are scheduled for the same nominal time, THEN the assessments should occur in the following order before administration of study treatment:
 - 1) Patient- reported outcome (PRO) assessments
 - 2) 12-lead ECG
 - 3) vital signs
 - 4) blood draws

Note: The timing of the assessments should allow the blood draw to occur at the exact nominal time.

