Lung biomarkers		X ⁴										X		X	X	
Immunogenicity (anti-GSK3196165 antibody) ¹⁷		X ⁴			X		X					X		X	X	
Anti-GM-CSF auto-antibodies		X ⁴														
Study Treatment GSK3196165/placebo ¹⁸		X		X	X	X	X	X	X	X						

ACPA: Anti-cyclic citrullinated protein antibody, CCP: Cyclic citrullinated peptide, ESR: Erythrocyte sedimentation rate, FVC: Forced vital capacity, HAQ-DI: Health Assessment Questionnaire Disability Index, HBV: Hepatitis B virus, HDL: High-density lipoprotein, LDL: Low-density lipoprotein, RF: Rheumatoid factor.

1. All subjects who withdraw from the study should have an early withdrawal (EW) visit as soon as possible after study agent discontinuation and then return for a follow-up visit (the last visit) for 10 weeks (12 weeks after last dose of study medication).
2. The same individual (where possible) should perform all disease assessments for an individual subject.
3. PRO assessments should be conducted before any tests, procedures, assessments or consultations, to avoid influencing the subjects' perception.
4. Assessments may be performed up to 24hours before dosing GSK3196165/placebo.
5. All safety evaluations should be conducted before dosing GSK3196165/placebo.
6. Height will be measured at only screening.
7. Complete physical at screening, and then limited physical examination (see Section [7.4.7](#)) thereafter.
8. ECG should be performed before vital signs, blood draws, and dosing (triplicate ECGs required at screening, and single thereafter unless there are safety concerns, in which case repeats may be required(see Section [7.4.9](#)).
9. Only SAEs related to study participation or related to a GSK product will be recorded from the time a subject consents to participate in the study.
10. Unless performed within previous 12 weeks (No need to repeat if subject re-screened).
11. Chest HRCT if $D_{LCO} \geq 60\% - <70\%$ predicted (No need to repeat if subject re-screened).
12. ≥ 8 hours fasting required before blood draw.
13. For women of child-bearing potential. S=serum; U=urine.
14. ESR measured locally.
15. PK sampling should be collected before dosing at the visits scheduled study treatment (GSK3196165/placebo). At the visits doesn't scheduled study treatments, it may be collected in any time during the visit. (Day 3, 74, 85, 106, 127, 155, and early withdrawal visit).
16. In consenting subjects.

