### 8.1.3. Immunogenicity Analyses

The immunogenicity analyses will be based on the Immunogenicity population, unless otherwise specified.

The positive subjects of Anti-GSK3196165 Binding Antibody Detection are defined as those of which tests at Confirming are “positive”, and otherwise negative. The positive subjects of Neutralising Antibody detection are defined those of which tests at Screening are “positive”, and otherwise negative.

The number and percentage of positive and negative subjects will be summarized. Shift table from baseline to every assessment will be produced to assess the number of subjects going from:

- negative→negative
- negative→positive
- positive→negative
- positive→positive

Anti-GSK3196165 Binding Antibody Detection (positive/negative) will be listed together with titre value (mL) and Rheumatoid Factor (positive/negative) for each subject with at least one positive result of Anti-GSK3196165 Binding Antibody Detection.

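### SAP 8.1.3 calls every unconfirmed ADA result negative, without checking on-treatment samples against drug level or an unstated assay tolerance

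*Protocol*

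**What the plan says.** Anti-drug antibody (ADA) is a secondary endpoint (Protocol 3, SAP 2.2).

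**Assay.** Protocol 7.5: "The presence of treatment emergent anti-drug antibodies (ADA) will be determined using a GSK3196165 bridging style ADA assay". Testing has screening, confirmation and titre tiers, with a cut point fixed at validation. Neither document states a drug-tolerance limit or says how the method deals with circulating drug.

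**Timing.** The row headed "Immunogenicity (anti-GSK3196165 antibody" in the Protocol 7.1 table gives baseline, Day 15, Day 29, Day 85, the final follow-up visit and early withdrawal. Protocol 7.5 puts follow-up testing of withdrawn subjects 12 weeks after the last dose; for a completer that is Day 71 + 84 = Day 155. Dosing (Protocol 4.2): "There will be 5 weekly injections (Day 1, 8, 15, 22, 29), then every other week (EOW) injections at Day 43, 57 and 71". On dosing days blood is drawn first (Protocol 7): "THEN the assessments should occur in the following order before administration of study treatment". PK is sampled at every ADA visit.

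**Analysis.** SAP 8.1.3 defines a positive subject by the confirmatory test and treats all others as negative. "The number and percentage of positive and negative subjects will be summarized", and "Shift table from baseline to every assessment will be produced to assess the number of subjects going from" each of the four combinations of negative and positive. The listing covers only subjects with at least one positive result. It shows titre and rheumatoid factor, not drug concentration.

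**Positivity rule.** Protocol 7.5 and SAP 11.5.5 call a post-dose sample treatment-emergent positive once it reaches the cut point. SAP 8.1.3 requires confirmation.

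**The concern.** A bridging assay needs free binding sites on the antibody being measured, and circulating drug can occupy them. A negative result in a sample with a high drug level can therefore mean either that no antibody is present or that it is masked. The plan has no category for the second case.

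Three of the four scheduled post-dose samples fall in the treatment period. If masking occurs at those visits, ADA that has gone by follow-up is missed. The shift table can also show a change from negative to positive at Day 155 that reflects drug washout and not late onset. An early-withdrawal sample is taken soon after stopping, so drug may still be present. A withdrawn subject who misses the 12-week sample is then called negative on drug-exposed samples alone.

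The concentrations needed to judge this are collected at the same visits. The plan nowhere sets them beside a never-positive subject's ADA result.

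**Working it through.** **1. Inputs.** Protocol Table 1 gives simulated median AUCs for 180 mg SC. The row "Last dose in Induction phase (Week 4-5" has AUC(0-168) = 1536 µg·hr/mL, and "Last dose in Maintenance phase (Week 10-12" has AUC(0-336) = 1930 µg·hr/mL.

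**2. The plan's own figures reproduce.** 48963/1930 = 25.4 and 5644/1930 = 2.9, matching the stated 25-fold and 3-fold margins. The average concentrations are 1536/168 = 9.1 and 1930/336 = 5.7 µg/mL at 180 mg. Substantial drug on treatment is therefore expected without any further modelling.

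**3. Levels at the ADA visits.** I summed a one-compartment curve with first-order absorption over the eight doses:

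C(t) ∝ Σ ka/(ka − ke) · [exp(−ke(t − s)) − exp(−ka(t − s))], over dose times s = 0, 7, 14, 21, 28, 42, 56, 70 days.

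The absorption rate ka is not given, so I assumed a range from 0.15 per day to near-bolus. For each ka, ke was solved so that the two AUCs stand in the ratio 1536/1930, and the curve was then scaled to 1930. The implied half-life is 10.2 to 13.5 days. Doses of 45 and 90 mg are scaled in proportion. Results in µg/mL, pre-dose where a dose is due:

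| Dose | Day 15 | Day 29 | Day 85 | Day 155 |
|---|---|---|---|---|
| 45 mg | 1.2–1.3 | 1.7–2.1 | 1.0–1.2 | 0.01–0.03 |
| 90 mg | 2.3–2.7 | 3.5–4.1 | 2.0–2.4 | 0.03–0.05 |
| 180 mg | 4.7–5.3 | 7.0–8.3 | 3.9–4.8 | 0.05–0.11 |

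As a check, Protocol 4.5 expects a steady-state trough of about 2 µg/mL or greater at 90 and 180 mg. The model's 90 mg value at Day 85 is 2.0 to 2.4.

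**4. Sensitivity.** With half-lives of 7 to 25 days imposed and only the 1930 figure matched, the three on-treatment samples span 0.7 to 9.5 µg/mL and Day 155 is at most 0.8. Most of those half-lives do not reproduce 1536.

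**5. Against an unknown tolerance T.**
- T below about 1 µg/mL: typical levels exceed it on treatment in all three active arms.
- T between about 1 and 8: the effect grows with dose. At an assumed T of 3, 45 mg is clear at all three visits, 90 mg exceeds T at Day 29 only, and 180 mg exceeds it at all three.
- T above about 8: typical levels stay below it everywhere.

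**6. Illustration of a consequence.** Suppose a fraction p of an arm of 10 has ADA on treatment only, and the assay detects a share s of them (both assumed). Then P(0 of 10 seen) = (1 − p·s)^10. For p = 0.2:
- s = 1: 0.8^10 = 11%
- s = 0.5: 0.9^10 = 35%
- s = 0.25: 0.95^10 = 60%

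**The case against.** The strongest reply is that harm depends on a figure outside these documents. Protocol 7.5 refers to an approved, validated method, and if its tolerance is above the levels seen, nothing is lost. That stands. A reader might infer that ADA incidence is under-read, and most so at 180 mg. The documents do not show this, because a dose gradient is expected mainly if tolerance lies between about 1 and 8 µg/mL.

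A reader might also blame the rule that unconfirmed results count as negative. Calling a screen-positive but unconfirmed sample negative is ordinary tiered testing and has nothing to do with drug interference. The gap is narrower: a negative obtained above the assay's tolerance is treated like any other negative.

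The design also mitigates the problem. Day 155 is nearly drug-free and already has its own place in the shift table. Withdrawn subjects are due a sample 12 weeks after the last dose, and qualifying hypersensitivity reactions trigger extra samples at the event and 12 weeks later. This stands for persistent ADA. It does not cover transient ADA, onset timing, or a missed 12-week sample.

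Nor is the PK information unused: concentrations are analysed and listed (SAP 7.1.3.2, Listing 59). They are only not linked to ADA.

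Finally, the stakes are modest. Reporting is descriptive, no hypothesis is tested, and with 10 per arm the exact interval for 1/10 is 0.3% to 44.5% (Protocol Table 4). That limits the severity but does not justify an on-treatment negative that cannot be interpreted.

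**Conclusion.** The point holds as a gap in the analysis rule, not as demonstrated bias. Three of four scheduled post-dose ADA samples are expected to carry about 1 to 8 µg/mL of drug: about 1 to 2 at 45 mg and 4 to 8 at 180 mg. The plan gives no means of telling an informative negative from an uninformative one. Whether any result is affected turns on the unstated drug tolerance, within the bands in step 5. Persistent ADA should be found at Day 155, at about 0.1 µg/mL or less. The exposure is limited to transient ADA, apparent time of onset, and subjects with no 12-week sample.

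The concentrations rest on linear PK, one compartment, an assumed absorption range, and medians simulated from an earlier study with a two-compartment model. Individual subjects will vary around them, and ADA could itself lower drug levels. The fix does not depend on the model, because it uses each subject's measured concentration.

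The conflict between the cut-point rule and the confirmation rule needs no assumption: the same sample can be positive under SAP 11.5.5 and negative under SAP 8.1.3.

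**What to change.** In SAP 8.1.3:

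- State the assay's validated drug tolerance. If it exceeds the concentrations measured at the ADA visits, one sentence saying so closes the interference question.
- Merge each ADA result with the same-visit GSK3196165 concentration. Set placebo to zero, since placebo samples are not assayed (Protocol 7.3).
- Class a negative whose concentration exceeds the tolerance as inconclusive.
- Tabulate positive, negative and inconclusive counts by visit and dose over all subjects tested. Keep inconclusive results in the denominator. Dropping them while keeping every positive inflates incidence: 1 positive and 9 inconclusive would read 1/1 = 100% instead of 1/10 = 10%.
- Label the Day 155 result as the one least affected by drug.
- List concentration beside the ADA result for all subjects, not only those with a positive.
- Reconcile the positivity rule across Protocol 7.5, SAP 11.5.5 and SAP 8.1.3, so that one definition feeds both the incidence and the shift table.

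The cost is SAP wording and one merge of data already collected, with no new samples. The downside is that fewer subjects can be called ADA-negative.
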